Patients who were classified as having negative bone scan and CT scan (estimated $\geq 90\%$ of patients) will undergo MRI (axial MRI and WB MRI) and F-18 NaF PET/CT. The outcome of these studies will be reported as 1) consistent with visible recurrence, 2) indeterminate 3) negative. In cases of findings consistent with visible recurrence or indeterminate a biopsy of the lesion of interest will be recommended if feasible. Any enrolled patient without a positive biopsy will be followed and their treatment (at discretion of treating physician), PSA values and outcome will be recorded to evaluate the scan result specificity and sensitivity in relation to additional information provided with follow-up (e.g. if patients undergo Salvage Radiation Therapy, PSA response will be recorded which will have significant implication in the interpretation of radiologic findings (see 10). Subsequently all patients without biopsy proven metastasis will undergo follow up imaging studies (the type of imaging to be recommended by radiologist)) within 4-6 months to reassess any abnormalities in the context of time, ongoing therapy or no therapy.

Sample Size:

Total Sample size is 56. Anticipated accrual is 2-3 patients a month.

Estimated Duration of the Study

24 months

Summary of Subject Eligibility Criteria:

Patients with 2 PSA values ≥ 0.2 ng/mL at least 4 weeks after surgery will be evaluated. Patients who were started on androgen deprivation therapy will not be allowed on this protocol. Patients who have started radiographic evaluation and underwent CT scan and/ or BS prior to registration to the study will be able to participate under a late registration provision, provided that WB/axial MRI and F-18 NaF PET/CT can be completed within 4 weeks of the CT scan and BS.

Investigational Product Dosage and Administration:

Not Applicable.

Clinical Observations and Tests to be Performed:

CT of the chest, abdomen and pelvis and bone scan. Targeted X Rays if suggested by the radiologist. If negative, WB/axial MRI and F-18 Sodium Fluoride PET /CT. Biopsy of suspected lesions will be performed if feasible, and repeat scans will be performed for patients with suspicious lesions.

Statistical Considerations:

Sponsor/Licensee:

City of Hope

Case Report Forms

Table of Contents

SECTION	PAGE
1.0 Objectives	8
2.0 Background.....	9
2.1 Introduction/Rationale for Development	9
2.2 Overview of Proposed Study	11
3.0 Patient Eligibility	12
3.1 Inclusion Criteria	12

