2.0 Background

2.1 Introduction/Rationale for Development

Background

Each year, approximately 32,000 men in the United States will have a recurrence of prostate cancer (PC) after radical prostatectomy.¹ For most of these patients the only manifestation of recurrent disease is an increasing level of serum prostate specific antigen (PSA) in the blood detected through routine monitoring after surgery. A PSA level of ≥ 0.2 ng/mL is considered the threshold for biochemical recurrence.² For those patients who have a recurrence, some will have disease that is initially confined to the prostate bed and pelvis. Patients who have not previously received adjuvant radiation therapy (RT) can potentially be cured by local salvage RT. However, this treatment approach is complicated by the inability to distinguish between those patients with an isolated local recurrence and those patients with occult distant metastases who will not benefit from salvage RT.^{3,4} Therefore accurate localization of recurrent disease has significant therapeutic implications.

Currently, there is no consensus regarding the use of specific imaging techniques in patients with biochemically recurrent prostate cancer. National Comprehensive Cancer Center (NCCCN) guidelines suggest obtaining “+/- CT scan, +/- bone scan, +/- Ultrasound, +/- MRI” indicating lack of any meaningful guidelines. In addition, in 2011, the FDA approved F-18 NaF PET/CT for the detection of bone metastases for Medicare beneficiaries through the Coverage with Evidence Development/National oncologic PET Registry program (NOPR) adding to the available options with limited guidelines.

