2.2 Overview of Proposed Study

After informed consent is obtained, patients will be screened for eligibility. Eligible patients will be registered for a study. The 6-year probability of progression-free survival based on the Memorial Sloan Kettering Cancer Center salvage RT PC nomogram will be recorded. Patients will then undergo imaging studies including CT of the chest, abdomen and pelvis. Targeted X-rays (TXR) will be obtained in case of equivocal findings if suggested by the radiologist. Patients who have CT scan and or bone scan that are interpreted as positive or indeterminate will be managed in a standard way at the discretion of the treating physician. That will frequently include additional imaging modalities and therapy as appropriate. Patients with CT scan and bone scan that are interpreted as negative (estimated $\geq 90\%$) will undergo WB/axial

MRI scan and 18-F NaF PET/CT scan. All imaging studies should be ideally completed within a 4-week period, although up to 8 weeks will be allowed.

One of the possible outcomes will be assigned to WB/axial MRI scan, and F18 NaF PET/CT scan: 1) consistent with visible recurrence 2) indeterminate 3) negative. In cases when the combination of WB/axial MRI and 18-F NaF PET/CT scan are interpreted as consistent with recurrence or indeterminate biopsy of the lesion of interest will be recommended if feasible (The presence of histologically proven metastasis will be considered the “gold standard” for the confirmation of metastasis, while recognizing that such confirmation will be rarely achieved.). Fifty six patients will be evaluated over 24 months.

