10.1 Verification of Scan Results

10.1.1 Biopsy of Suspected Metastases

Biopsy of metastatic sites of prostate cancer patients is feasible.²⁷ Bone biopsies of patients with known, advanced metastatic prostate cancer are performed with increasing frequency with yield exceeding 50 % (personal communications, [name] , University of Michigan) We estimate that in our population of patients biopsies will be accomplished in approximately 25% of cases of suspicious lesions because of their likely small size or difficult location and targeting . Based on our personal experience and personal communications we anticipate extremely high willingness of patients to undergo biopsy of suspected lesions.

The presence of histologically proven metastasis will be considered the “gold standard” for the confirmation of metastasis. However since majority of patients will not be able to undergo biopsies we will utilize two additional strategies to confirm the interpretation of imaging studies.

10.2.PSA Response To Salvage Radiation Therapy

The majority of our population of patients (unless biopsy proven metastases are discovered) will be offered salvage radiation therapy to the prostate bed. The concept of this therapy is that all the recurrent cancer cells may be located in the radiation field around prostate bed. Therefore the expected result of salvage RT is PSA level becoming undetectable (<0.04 ng/dL) within 6-8 weeks following completion of therapy.

Possible scenarios:

- a) The undetectable PSA level following salvage RT would be a very strong indicator that any visible abnormalities outside of the radiation field are false positives. If those lesions were “real” metastases (even extremely small) they would be expected to produce detectable amounts of PSA.
- b) If PSA does not become undetectable (< 0.04 ng/dL) in patients with completely normal scans that would be considered false negative.
- c) In patients who have abnormalities visible on the scans and inwhom salvage RT to prostate bed does not result in undetectable PSA level, then it is highly likely that the visible lesions are indeed true positives (likely sources of persistent PSA elevation). This scenario is the most difficult to interpret, because it is possible (but in my opinion much less likely) that the source of PSA is related to invisible metastases and identified lesions are benign.

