10.2 Follow-up scans

Evolution of lesions over the period of time provides invaluable help in the verification of original interpretation of the scans even in the absence of biopsy. Therefore all the patients will undergo follow up scans (the type advised by radiologist) 4-6 months after registration to the protocol. These scans will be interpreted in the context of ongoing therapy (i.e. hormonal therapy) or observation. Several possible scenarios will allow us to interpret and verify the findings on the original scans.

- a) The persistence, growth, increase in numbers and intensity of enhancement of lesions in patients on observation would strongly favor the interpretation of a true positive finding.
- b) Complete stability over time or resolution of lesions without ongoing therapy would strongly favor false positive interpretation.
- c) Evolution of lesions (regression, radiologic signs of healing in the context of ongoing hormonal therapy (and lack of any history of trauma) would strongly support the interpretation of true positive scans
- d) Complete stability of lesions despite ongoing hormonal therapy would favor false positive interpretation

By combining these three elements of verification of original interpretation of WB/axial MRI and F-18 NaF PET/CT we will be able to provide the most robust assessment of sensitivity and specificity of these imaging modalities in the literature that may prove to be quite useful in the management of patients with biochemically recurrent prostate cancer.

Table 1

Interpretation of Imaging with WB/axial MRI and F-18 NaF PET/CT based on subsequent biopsy, therapy and follow up imaging (not all patients will be classified as below depending on additional systemic therapy given)

Original MRI/PET Interpretation	Biopsy	PSA response to salvage RT	Follow up scans	FINAL Interpretation of Baseline MRI/PET	
Mets	+	NA	Regardless	TP	
			Mets	Indeterminate	
			Indeterminate	FP	
			No mets	FP	
		≥ 0.04	Mets	TP	
	- or NA		Indeterminate	TP	
			No mets	Indeterminate	
	NA	Mets	TP		
		Indeterminate	TP		
		No mets	FP		
Indeterminate	+	NA	Regardless	TP	
			Mets	Indeterminate	
			Indeterminate	FP	
		≥ 0.04	No mets	FP	
			Mets	TP	
	- or NA	≥ 0.04	Indeterminate	TP	
			No mets	Indeterminate	
		NA	Mets	TP	
			Indeterminate	Indeterminate	
			No mets	FP	
Negative	N/A	<0.04	Mets	Indeterminate	
			Indeterminate	TN	
			No mets	TN	
		≥ 0.04	Mets	FN	
			Indeterminate	FN	
			No mets	Indeterminate	
		NA	Mets	Indeterminate	
			Indeterminate	TN	

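### The final-interpretation Table 1 omits scenario (a)'s outside-the-field condition, so a lesion that was irradiated and cleared can be scored a false positive

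*Combined protocol and SAP*

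**What the plan says.** Two subsections of section 10 carry the number 10.2. The first, on PSA response to salvage RT, states that most patients without biopsy-proven metastases "will be offered salvage radiation therapy to the prostate bed". It adds that "the expected result of salvage RT is PSA level becoming undetectable (<0.04 ng/dL) within 6-8 weeks following completion of therapy". Scenario (a) then reads an undetectable PSA as a very strong sign that "any visible abnormalities outside of the radiation field are false positives". The reason given is that a real metastasis, however small, would be expected to go on producing detectable PSA.

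The second, on follow-up scans, ends with the table that assigns the final class: "Interpretation of Imaging with WB/axial MRI and F-18 NaF PET/CT based on subsequent biopsy, therapy and follow up imaging". Its inputs are the baseline read, the biopsy result, PSA after salvage RT and the follow-up scan. The one exemption it states is that "not all patients will be classified as below depending on additional systemic therapy given".

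Three other places bear on where a visible lesion may lie:

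- Section 2.1 says of men who recur that "some will have disease that is initially confined to the prostate bed and pelvis", and that men without earlier adjuvant RT can potentially be cured by local salvage RT.
- Section 2.2 reads the newer scans as "1) consistent with visible recurrence 2) indeterminate 3) negative", a scale that is not limited to distant sites.
- The synopsis says that for enrolled patients without a positive biopsy "their treatment (at discretion of treating physician), PSA values and outcome will be recorded".

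**The concern.** Scenario (a) is sound only because of its location condition. RT to the field cannot have removed PSA produced by a lesion outside it, so an undetectable PSA counts against such a lesion being cancer. For a lesion inside the field the argument fails: a true recurrence that was irradiated would also clear and leave PSA undetectable. The table applies the conclusion without the condition.

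The second 10.2 subsection promises estimates of sensitivity and specificity, and these rest on the table's classes. A true detection scored FP adds to the denominator of both specificity, TN/(TN+FP), and positive predictive value, TP/(TP+FP), without adding to either numerator. The error is also selective, since it falls on men in whom the newer scans showed disease that RT then controlled.

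**Working it through.** The plan gives no figure for this point. The main check is a comparison of the scenario with the table, followed by a rough size.

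**1. Which rows apply.** In the Mets and Indeterminate blocks, three rows stand between the positive-biopsy row and the PSA ≥0.04 rows. Their PSA label does not survive in the text available. The intact Negative block runs <0.04, ≥0.04, NA, so these are taken to be the <0.04 rows. They read:

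| Baseline read | Biopsy | PSA after RT | Follow-up scan | Final class |
|---|---|---|---|---|
| Mets or Indeterminate | − or NA | <0.04 | Mets | Indeterminate |
| Mets or Indeterminate | − or NA | <0.04 | Indeterminate | FP |
| Mets or Indeterminate | − or NA | <0.04 | No mets | FP |

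FP therefore appears in four cells: two baseline reads times two follow-up results.

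**2. Literal application to two constructed men.** Both have a baseline Mets read, no biopsy, PSA <0.04 after RT and follow-up No mets.

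- Lesion in a rib, outside the field: the table gives FP, and scenario (a) supports it.
- Lesion inside the irradiated volume: the table gives FP, and scenario (a) does not support it.

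**3. Consistency with the follow-up scenarios.** The second 10.2 subsection lets resolution of a lesion favour FP only when there is no ongoing therapy, and counts regression under hormonal therapy as support for a true positive. Reading resolution after irradiation of the same lesion as FP does not fit that reasoning.

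**4. Possible size.** Inputs:

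- about 49 men negative on standard scans, and a true positive rate of 15% (section 12);
- biopsy achieved in about 25% of suspicious lesions (section 10.1.1), so 75% without;
- all unbiopsied positives are true and receive salvage RT, and follow-up is read No mets or Indeterminate (assumption);
- 20% to 50% of these lesions lie inside the field (assumption; the documents give no figure);
- 10% to 50% reach undetectable PSA (section 2.1's long-term success of salvage RT, used as a proxy for PSA <0.04 at 6-8 weeks).

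Expected positives: 49 × 0.15 = 7.35. Without biopsy: 7.35 × 0.75 = 5.51.

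| Case | In field | PSA <0.04 | Men mis-scored | Share of positives |
|---|---|---|---|---|
| Low | 0.20 | 0.10 | 5.51 × 0.02 = 0.11 | 0.75 × 0.02 = 1.5% |
| Middle | 0.35 | 0.30 | 5.51 × 0.105 = 0.58 | 0.75 × 0.105 = 7.9% |
| High | 0.50 | 0.50 | 5.51 × 0.25 = 1.38 | 0.75 × 0.25 = 18.75% |

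Baseline Indeterminate reads are not counted and would add to these figures. Counts are small, so one man matters: 1/7.35 = 13.6% of the expected positives.

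**5. Does it reach the primary rule?** Section 12's rule reproduces. With n = 45 and at least 4 positives, the exact binomial gives a type I error of 4.6% at a 3% rate (stated: less than 5%) and power of 92.2% at 15% (stated: greater than 86%). If, and only if, table FPs were subtracted from the success count, the high case would lower the rate to 0.15 × (1 − 0.1875) = 12.19%. Power for at least 4 positives would then be 81.5% at n = 45 and 86.3% at n = 49. In the low case at n = 45 it would be 91.6%.

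**The case against.** The strongest reply is that the condition is already implicit. Section 10 describes RT to the prostate bed, the table's first column says Mets rather than recurrence, and the objectives separate metastatic disease from prostate-bed recurrence. Under prostate-bed RT, a lesion called Mets is ordinarily outside the field, which is the case scenario (a) covers. Much of this stands. It makes the problem uncommon, and an irradiated pelvic node is only a possibility, because the protocol gives no field borders and nowhere says that nodes are treated.

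It does not remove the gap. No rule maps a read of visible recurrence to the table's Mets. The Indeterminate block has no site limit. A secondary objective expects MRI to show prostate-bed recurrence that CT misses. Scenario (a) would not need its qualifier if every visible abnormality lay outside the field.

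A second reply is that the <0.04 label on the decisive rows is inferred. That is so, but the order of the Negative block makes the inference secure.

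A reader might also infer that the trial could miss its success criterion: one man lost from the minimum of 4 of 45 (8.9%) leaves 3 of 45 (6.7%), below the 8% mark, or power falls below the stated 86%. The documents do not support this. Section 12 counts men found positive on the newer scans. It says that follow-up and treatment results will be evaluated in the final determination, not that table FPs are subtracted. The fall below 86% also needs the worst-case inputs combined with n = 45; at the n = 49 behind the expected count, power stays at 86.3%.

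**Conclusion.** The concern holds as an inconsistency between a stated rationale and the rule meant to carry it out. For an unbiopsied or biopsy-negative lesion inside the irradiated volume, such as a prostate-bed or adjacent pelvic lesion read as recurrence or indeterminate, the table can return FP where the protocol's own argument does not.

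What is biased is the FP and TP counts, and so the specificity and positive predictive value. The number of men is unknown. The range of 0.1 to 1.4 rests on an assumed in-field share and a proxy for PSA response, and about one man or fewer is the likely scale. No effect on the 4-of-45 rule, the 8% mark or the stated power is established. The change is worth making because the table yields a wrong class in a foreseeable case and the repair is small.

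**What to change.** Carry scenario (a)'s condition into the table. For a baseline Mets or Indeterminate read without a positive biopsy and with PSA <0.04 after salvage RT, assign FP only when the lesion or lesions behind the baseline read lie outside the irradiated field. Otherwise assign Indeterminate, with the note that the read cannot be assessed by PSA response. Add one case report form item, lesion inside RT field: yes / no / unknown, completed from available RT records. An unknown answer also leads to Indeterminate.

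The cost is one line in the table and one data item, with no extra scans, readers or patients. A few men move from FP to Indeterminate, so slightly fewer have a resolved class. Salvage RT is not a study procedure and the protocol does not say that RT plans are collected, so field information may be missing for some men. The number classed Indeterminate for this reason should be reported beside the accuracy estimates.

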Classically, the terms sensitivity and specificity are used in evaluating diagnostic tests. However, it is infeasible to know if microscopic metastatic disease was missed when the scans are negative, and as a result the human studies comparing MRI to bone scan and targeted X-rays use a measure of “sensitivity” (based on “best valuable comparator (BVC)”) that only conveys that the MRI is superior to bone scan and targeted X-rays. In a study by Lecouvet et al.¹⁷ 66 patients with high-risk prostate cancer were evaluated with standard bone scan and X-rays and MRI of the axial skeleton. BVC was a panel of reference consisting of the CT correlation of equivocal MRI findings, prospective systematic follow-up bone scan and MRI studies at 6 months, and clinical and biologic follow-up obtained during 6 months of follow-up. MRI did not incorrectly declare any patient to have metastatic disease out of the 25 without evidence of metastasis at initial staging based on final BVC attribution. In addition, of the 41 patients determined to have metastatic disease by BVC, all 41 were positive on MRI, suggesting that MRI did not miss any lesions identified by other scans. More importantly, 7 of the 23 (30%) of patients who would have been considered negative with bone scan and targeted X-rays were determined to have metastatic disease on MRI, and considered positive by BVC. Combined, this demonstrates that MRI has high specificity (no false positive calls), did not miss any positive findings on bone scan and X-ray, and was able to visualize evidence of metastatic disease in 30% of the patients deemed negative on bone scan and X-ray. As a result, there is a general consensus about the superiority of MRI techniques over bone scan in the detection of bone metastases, although the high sensitivity quoted in the literature is known to not relate to the more classic definition of sensitivity (e.g. sensitivity to detect a known lesion of a certain size) and the quoted specificities also need further evaluation.

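### Without salvage RT, Table 1 scores the same follow-up scan by the baseline read and allows no false negative; the text also conflicts with the table on persistent PSA after RT

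*Combined protocol and SAP*

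**What the plan says.** The synopsis states that treatment, PSA and outcome in patients without a positive biopsy "will be recorded to evaluate the scan result specificity and sensitivity in relation to additional information provided with follow-up". Section 10.2 Follow-up scans claims that "we will be able to provide the most robust assessment of sensitivity and specificity of these imaging modalities in the literature". The only rule for deriving either measure is the Table 1 that closes that section (sections 7.4 and 9.0 each have another Table 1). Its caption is "Interpretation of Imaging with WB/axial MRI and F-18 NaF PET/CT based on subsequent biopsy, therapy and follow up imaging", with the caveat "not all patients will be classified as below depending on additional systemic therapy given". It crosses the baseline read, biopsy, PSA after salvage RT (below 0.04, at or above 0.04, or NA, which I read as no salvage RT) and the follow-up scan. Each combination becomes TP, FP, TN, FN or Indeterminate.

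Scenario (b), under PSA Response To Salvage Radiation Therapy, reads: "If PSA does not become undetectable (< 0.04 ng/dL) in patients with completely normal scans that would be considered false negative". It sets no condition on the follow-up scan.

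Section 1.0 does not list sensitivity or specificity as an objective. Section 12.0 gives no estimator for them and no rule for Indeterminate results.

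**The concern.** A reference standard should give the same verdict on the same evidence, whatever the index scan said. In the no-RT rows it does not: follow-up imaging alone can confirm a suspicious baseline scan but can never show that a negative one missed disease. An unresolved follow-up scan also counts as a true negative only because the baseline was negative, which feeds specificity.

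Missed disease is the central issue here. Section 2.1 puts occult metastases at 50-90% of these patients, and section 12.0 at more than half. The conflict over scenario (b) means that two analysts following the protocol could code the same patient differently. Section 12.0 also says that the final judgement of success will weigh follow-up scans and treatment results, so these classifications may colour the conclusion.

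**Working it through.** The documents state no sensitivity figure to reproduce. The cells come first, then illustrations.

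**1. No-RT rows, no positive biopsy.**

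| Follow-up scan | Baseline Mets | Baseline Indeterminate | Baseline Negative |
|---|---|---|---|
| Mets | TP | TP | Indeterminate |
| Indeterminate | TP | Indeterminate | TN |
| No mets | FP | FP | TN |

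The nine Negative rows are complete in the text I read. The Mets / NA rows are shifted by text extraction. The Indeterminate block has also lost its first PSA label, so the placement of its NA label is an inference, though a natural one. The argument does not need the Mets column.

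**2. FN cells.** FN appears twice, both times for a Negative baseline with PSA ≥0.04 after RT (follow-up Mets or Indeterminate). Without RT, FN = 0. With Indeterminates excluded, sensitivity among classified no-RT patients is TP/(TP + 0) = 100% whenever there is one TP.

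**3. Text against table.** For a normal baseline with PSA ≥0.04 after RT, scenario (b) gives FN always. The table gives FN, FN and Indeterminate for follow-up Mets, Indeterminate and No mets.

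**4. Illustration A: the no-RT rule alone.** From the documents: 45 patients and 15% detected (section 12.0), and occult metastases 50-90% (section 2.1; 70% used). Assumed: RT share r = 0.70; all metastatic RT patients keep PSA ≥0.04; follow-up 15% Mets, 15% Indeterminate and 70% No mets for detected and missed patients alike; no positive biopsies; no FN among non-metastatic patients.

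- Detected d = 45 × 0.15 = 6.75; diseased = 45 × 0.70 = 31.5; missed m = 24.75. True sensitivity = 6.75/31.5 = 21%.
- Table as read: TP = 6.75 × 0.30 = 2.03; FN = 24.75 × 0.70 × 0.30 = 5.20; 2.03/(2.03 + 5.20) = 28%. In general this is d/(d + m × r).
- At r = 0.90: 6.75/(6.75 + 24.75 × 0.90) = 23%.
- If the shifted Mets / NA / Indeterminate cell is really Indeterminate: TP = 6.75 × (0.70 × 0.30 + 0.30 × 0.15) = 1.72; 1.72/(1.72 + 5.20) = 25%.
- NA rows scored alike (follow-up Mets as FN for a Negative baseline, and follow-up Indeterminate as Indeterminate throughout): FN = 5.20 + 24.75 × 0.30 × 0.15 = 6.31; 1.72/(1.72 + 6.31) = 21%.
- Over occult 50-90% and RT 50-90%, the table gives 18-46% (17-39% on the cautious cell reading) against a true 17-30%.

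**5. The disputed scenario (b) cell.** In illustration A it holds 24.75 × 0.70 × 0.70 = 12.1 of 45 patients. Coding only that cell FN gives 2.03/(2.03 + 5.20 + 12.13) = 10%, against 28% with the table's coding.

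**6. Illustration B: a different follow-up pattern.** 49 patients, 50% occult, 15% detected: d = 7.35, m = 17.15, true 30%. Assumed: 70% RT; follow-up of detected patients 80/20/0 (Mets/Indeterminate/No mets) and of missed patients 40/20/40.

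- Table: FN = 17.15 × 0.70 × 0.60 = 7.20; 7.35/14.55 = 51%.
- NA rows scored alike: TP = 7.35 × (0.70 + 0.30 × 0.80) = 6.91; FN = 7.20 + 17.15 × 0.30 × 0.40 = 9.26; 43%.
- Only the scenario (b) cell as FN: 7.35/(7.35 + 17.15 × 0.70) = 38%.

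**7. Offsetting cells.** A no-RT positive with No mets at follow-up is FP. A non-metastatic patient with a local RT failure, negative baseline and indeterminate follow-up is FN.

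- In illustration A, non-metastatic RT patients number (45 − 31.5) × 0.70 = 9.45. If about 2.2 of them fell in the FN cell, the estimate would be 2.03/(2.03 + 5.20 + 2.2), back to about 21%.
- A strong version of both offsets in illustration B's population: 90% RT; follow-up of detected patients 40/20/40 and of missed patients 90/10/0; half of non-metastatic RT patients with PSA ≥0.04, 30% of those with indeterminate follow-up. TP = 7.35 × 0.60 = 4.41; FN = 17.15 × 0.90 + 24.5 × 0.90 × 0.50 × 0.30 = 18.74; 4.41/23.15 = 19% against a true 30%.

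**The case against.** A reader might infer that the promised sensitivity is biased upward. The documents do not support that. It presumes TP/(TP + FN) with Indeterminates dropped, an estimator the plan never states, and step 7 shows that other cells can reverse the sign. It would be equally wrong to infer that aligning the NA rows restores the truth, or that coding the scenario (b) cell FN must overshoot: illustrations A and B disagree on both.

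Part of the asymmetry is principled. Section 10.2 Follow-up scans verifies a baseline lesion by its persistence or growth. A lesion first seen at 4-6 months may be new, so Indeterminate for Negative / NA / Mets is defensible. That argument does not reach TN for an unresolved follow-up scan when an indeterminate baseline with the same follow-up stays Indeterminate.

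Scenarios (a) to (c) can be read as describing the PSA element alone, before the table combines all three elements. That makes the conflict mild, but (b) carries no such qualification.

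The affected group may be small. The protocol says: "The majority of our population of patients (unless biopsy proven metastases are discovered) will be offered salvage radiation therapy to the prostate bed". The caption also leaves some patients unclassified because of systemic therapy. With about 7 classified diseased patients in illustration A, chance swamps the shift: the exact 95% interval for 2 of 7 is 4-71%. Finally, section 2.1 already concedes that "it is infeasible to know if microscopic metastatic disease was missed when the scans are negative". All of this limits the size of the problem; none of it removes the inconsistency.

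**Conclusion.** The point holds as a should-fix inconsistency in the classification rules. Three parts are firm and need no assumption beyond the reading of the table: the same no-RT follow-up result is scored by the baseline read, so no FN is possible without RT; an unresolved follow-up scan after a negative baseline is called TN; and scenario (b) disagrees with the table in one cell.

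The size is not firm. Taken alone, the no-RT rule raises sensitivity (28% against 21% at 70% RT, 23% at 90%, in illustration A). The net direction depends on the RT share, follow-up yields and local RT failures, none of which the documents give. Unequal confirmation adds a further, separate push: section 10.1.1 estimates that "biopsies will be accomplished in approximately 25% of cases of suspicious lesions". If all of those were positive, illustration A would give TP = 0.25 × 6.75 + 0.75 × 2.03 = 3.21 and 3.21/(3.21 + 5.20) = 38%. That extra rise is not due to the no-RT rows.

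The 4-of-45 count, the sample size and the listed objectives do not depend on the FN cells.

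**What to change.** 1. Score Negative / NA / Indeterminate as Indeterminate, matching the Indeterminate-baseline row. If the source table confirms that Mets / NA / Indeterminate is TP, make it Indeterminate too. State that this could change which detections count as confirmed when section 12.0's final judgement of success is made.
2. Report sensitivity with Negative / NA / Mets counted as FN and, separately, as Indeterminate, and say that disease first seen at 4-6 months may be new.
3. Reconcile scenario (b) with the table so that one rule applies, and report sensitivity under the other coding as well.
4. Report sensitivity and specificity with Indeterminates excluded, then counting them as diseased and as disease-free. Do not call these bounds on the true values: in illustration A, 24.75 × 0.30 × 0.70 = 5.2 missed no-RT patients with No mets at follow-up are still scored TN after the change.

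The cost is one or two table cells, one clause in scenario (b) and a short analysis paragraph. The price is more Indeterminate results and a less precise, possibly lower, sensitivity.
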